# Confidence Intervals of Difference (P1-P2)

Interval	Estimated	Confidence	Confidence
Method	Value	Limit	Limit
Chi-Square	0.2561	0.1456	0.3666

(Pearson)

(The calculation results are presented in the language of the original source)

In view of the considered nosology and absence of significant factors requiring a conservative approach for determination of the non-inferiority margin, for this purpose we can use a two-sided CI 90%. In such a case, the lower limit for the rate difference (a two-sided CI 95%) will amount to 14.6%. Therefore, a margin of 14.5% is considered to be justified.

Based on the above, we may hypothetically expect a rate of positive response to a new

	therapy (absence of a sore throat as an efficacy measure) at least 63%. A statistic hypothesis tested:		
	H0: $p_1-p_2 \le -14.5\%$ compared to H1: $p_1-p_2 > -14.5\%$ If a null hypothesis is rejected, a conclusion will be made that efficacy of the study drug is not less than that of the comparator drug.		
	A sample size is evaluated based on the following assumptions:		
	- A rate of positive response to therapy (absence of a sore throat as an efficacy measure) in a comparator drug arm is 63%.		
	- A rate of positive response to therapy (absence of a sore throat as an efficacy measure) in a study drug arm is 65% (chosen within the tested hypothesis and based on the sample size and expected positive response).		
	- Power = 80%		
	- A non-inferiority margin: 14.5		
	- Significance level: 97.5%		
	- Randomization in 1:1 ratio (study drug : comparator drug). A number of patients required at 80% power and 2.5% one-sided significance level to prove the hypothesis of the study drug efficacy not more than 14.5% inferior to that of the comparator drug (determined by absence of a sore throat after 3 days of therapy) if 128 patients in every arm.		
Interim analysis	An interim analysis may be conducted after receipt of efficacy data for Angal and ANTI-ANGIN ® FORMULA, spray, after 3 days of therapy, on Day 4, for 100 patients in every arm. The interim analysis includes demographic data, data on the anamnesis and concomitant therapy, available data on efficacy and safety of Angal and ANTI-ANGIN ® FORMULA drugs.		
Blinding, randomization	This trial will be open, without blinding. The patients will be included by randomization in 1:1 ratio using envelopes at the trial site.		

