### 9.1.2. Analysis of the primary efficacy endpoint

The primary outcome measure in this trial was the proportion of patients without sore throat after 3 days of therapy, on Day 4, as evaluated by the Investigator according to the Tonsillopharyngitis Severity Score (TSS), in both Angal and ANTI-ANGIN® FORMULA arms.

A null hypothesis of this trial assumes that Angal, the study drug, is less effective than ANTI-ANGIN® FORMULA, the comparator drug. An alternative hypothesis of this trial assumes that Angal, the study drug, is not less effective than ANTI-ANGIN® FORMULA, the comparator drug.

14.5% is chosen as a non-inferiority margin (see Section 9.2 for a justification) based on the results of a randomized, placebo-controlled trial of a similar drug.

The group comparison will be carried out using the Fisher's exact test (one-sided test, in connection with the null hypothesis of non-inferiority).

For the proportion difference, the 90% confidence interval (CI) will be calculated according to the procedure described in Newcombe, Robert G. "Interval Estimation for the Difference Between Independent Proportions: Comparison of Eleven Methods," Statistics in Medicine, 17, 873-890 (1998).

Thus, the non-inferiority will be confirmed if the limit of the two-sided 90% confidence interval for the difference in the proportions will be 14.5% or lower.

A primary endpoint analysis will be conducted both for the ITT (main analysis) and PP populations (additional analysis).

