#### **Confidence Intervals of Difference (P1-P2)**

Interval	Estimated	Confidence	Confidence
Method	Value	Limit	Limit
Chi-Square (Pearson)	0.2561	0.1456	0.3666

(The calculation results are presented in the language of the original source, i.e., from NCSS 8 statistical program).

- This is a non-inferiority trial; therefore, a non-inferiority margin for the primary endpoint should be justified and amount to not more than 14.5%.
- An expected rate of positive response to therapy (absence of a sore throat as an efficacy measure) in a comparator drug arm is 63%.
- An expected rate of positive response to therapy (absence of a sore throat as an efficacy measure) in a study drug arm is 65% (chosen within the tested hypothesis and based on the sample size and expected positive response).
- A one-sided type I error ( $\alpha$ ) = 2.5 % (0.025)
- A type II error ( $\beta$ ) = 20% (0.2), which corresponds to 80% power.
- Expected discontinuation from the trial will amount to 10% during the treatment.

The tested hypotheses are worded as follows:

1. Null hypothesis (Ho): Difference in the primary endpoint achievement incidence while using Angal, the study drug, and ANTI-ANGIN® FORMULA, the original drug, for treatment of acute infectious and

inflammatory pharyngeal diseases will exceed 14.5% in favor of ANTI-ANGIN  $^{\circledast}$  FORMULA:

$$H_0: p_1 - p_2 \le -0.145$$

2. Alternative hypothesis (HA): Difference in the primary endpoint achievement incidence while using Angal, the study drug, and ANTI-ANGIN® FORMULA, the original drug, for treatment of acute infectious and inflammatory pharyngeal diseases will not exceed 14.5% in favor of ANTI-ANGIN® FORMULA

$$H_A: p_1 - p_2 > -0.145$$

Where p1 and p2 is the primary endpoint achievement incidence while using Angal, the study drug, and ANTI-ANGIN® FORMULA, the original drug, respectively.

To calculate a sample size in every group, one can use a formula presented by Chow S, Shao J, Wang H. 2008. Sample Size Calculations in Clinical Research. 2nd Ed. Chapman & Hall/CRC Biostatistics Series. page 90:

$$n = (p_1 \times (1 - p_2) + p_2 \times (1 - p_2)) \times \left(\frac{z_{1-\alpha} + z_{1-\beta}}{p_1 - p_2 - \delta}\right)^2$$

where:

- n = Size of one group;
- z = Normal distribution function at the set levels of  $\alpha$  and  $\beta$ ;
- $\delta$  = Non-inferiority margin;
- p1 = Expected proportion in Angal group;

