### 9.3 Applicable significance level

All statistical analyses in this trial will be conducted at 95% significance level (a threshold p value for confirmation of statistical significance is below 0.05), except for the primary endpoint where an one-sided statistical criterion will be used with 97.5% significance level (a threshold p value is below 0.025). The two-sided statistical criteria will be used for all other parameters.

For the primary endpoint evaluation, 90% CI will be calculated for the proportions difference with further evaluation of its lower boundary limit.

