# 4.1.2 Primary endpoint

The primary endpoint of the trial (absence of the sore throat after 3 days of therapy on Day 4) will be presented as the difference between the proportions for each arm. The group comparison will be carried out using the Fisher's exact test (one-sided test, in connection with the null hypothesis of non-inferiority). For the proportion difference, the 90% confidence interval (CI) will be calculated according to the procedure described in Newcombe, Robert G. "Interval Estimation for the Difference Between Independent Proportions: Comparison of Eleven Methods," Statistics in Medicine, 17, 873-890 (1998).

Thus, the non-inferiority will be confirmed if the limit of the two-sided 90% confidence interval for the difference in the proportions will be 14.5% or lower.

A primary endpoint analysis will be conducted both for the ITT (main analysis) and PP populations (additional analysis).

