#### 5.2 List of figures

# Figure 1. TSS scores changes by visits and trial arms

For the parameters listed below: pharyngalgia, difficulty in swallowing, salivation, hyperemia of pharyngeal mucosa, and body temperature increase, as well as for total sum of scores

Figure 2. Difference in proportions of patients who achieved efficacy criteria in every arm, 90% CI

Figure 3. Incidence of TSS scores decrease for 50% or more in the trial arms

Figure 4. A period of time required for disease signs resolution according to the patient's diary and the trial arms

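### The sentence that gives the numeric success criterion for the primary confidence interval contradicts the plan's own null hypothesis

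*Protocol*

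**What the plan says.** Protocol 9.1.2 sets the margin at 14.5%, calls for a 90% interval by a method from a cited paper that compares eleven, and then states that non-inferiority is confirmed "if the limit of the two-sided 90% confidence interval for the difference in the proportions will be 14.5% or lower". SAP 4.1.2 repeats the sentence unchanged. It is the only place in either document where a number is attached to the interval as a success criterion.

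Neither document fixes the direction of the difference at that point. SAP 4.1.2 says the endpoint "will be presented as the difference between the proportions for each arm", and the planned display in SAP 5.2 is listed as "Figure 2. Difference in proportions of patients who achieved efficacy criteria in every arm, 90% CI".

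Elsewhere the plan does define a signed scale:

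- Protocol 9.2 and SAP 3.9 state H0: p1 - p2 <= -0.145 and HA: p1 - p2 > -0.145, with the definition "Where p1 and p2 is the primary endpoint achievement incidence while using Angal, the study drug, and" the comparator. The synopsis has the same hypotheses.
- The worded alternative in Protocol 9.2 and SAP 3.9 says the difference in "inflammatory pharyngeal diseases will not exceed 14.5% in favor of" the comparator.
- Protocol 9.3 and SAP 3.10 say: "For the primary endpoint evaluation, 90% CI will be calculated for the proportions difference with further evaluation of its lower boundary limit". SAP 4 also names the lower limit. None of the three gives a threshold.
- The synopsis has a separate rule based on the test: "If a null hypothesis is rejected, a conclusion will be made that efficacy of the study drug is not less than" that of the comparator.

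**The concern.** This sentence converts the primary interval into the trial's conclusion, and SAP 4 says the non-inferiority claim rests on the primary parameter alone. A higher p1 - p2 favours Angal, so success should require the lower limit to lie **above** -14.5 points. The sentence instead requires a limit to lie **at or below** +14.5. Supplying the lower limit from Protocol 9.3 does not rescue it: a lower limit of 14.5% or less is met almost always when Angal is inferior. Supplying only the minus sign makes it worse, because a lower limit of -14.5% or less is the exact complement of rejecting H0.

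The realistic harm is a dispute at the primary analysis of an open-label trial over which limit, scale and sign apply. Read literally on p1 - p2, the sentence can err in both directions: it can confirm non-inferiority when H0 is not rejected, and deny it when H0 is rejected.

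**Working it through.** **Inputs.** Margin 14.5 points; comparator rate 63% and Angal rate 65% (Protocol 9.2); 128 evaluable per arm (Protocol 9.2); two-sided 90% interval (Protocol 9.1.2 and 9.3, SAP 4.1.2). At the margin, Angal = 63 - 14.5 = 48.5%. A further scenario, 75% v 63%, is added to show the opposite error.

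**Interval method, checked on the plan's own figure.** Protocol 9.2 reports 14.56 to 36.66% for 65/104 v 38/103. The Wald interval reproduces it:

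- difference = 0.6250 - 0.3689 = 0.2561
- SE = sqrt(0.6250 x 0.3750/104 + 0.3689 x 0.6311/103) = 0.0672
- 0.2561 ± 1.645 x 0.0672 = 0.1456 to 0.3666

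The Newcombe hybrid score interval for the same data is 14.23 to 36.06%. The citation therefore does not settle the method. I assume the hybrid score and check Wald as a sensitivity.

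**The rules compared.** Let L and U be the limits for p1 - p2. H0 is rejected when L > -0.145. The upper limit of comparator minus Angal is -L, and -L <= 0.145 means L >= -0.145. This differs from the H0 rule only at equality, which no outcome at 128 per arm produces.

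**Probability of declaring non-inferiority**, by full binomial enumeration over both arms, 128 per arm, 90% hybrid score:

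| Reading | 48.5% v 63% (margin) | 65% v 63% | 75% v 63% |
|---|---|---|---|
| (a) L > -14.5, matches H0 | 4.9% | 87.4% | 99.9% |
| (b) upper limit of comparator minus Angal <= 14.5 | 4.9% | 87.4% | 99.9% |
| (c) literal, L <= +14.5 | 100% | 100% | 98.1% |
| (d) literal, U <= +14.5 | 99.9% | 68.4% | 11.7% |
| (e) minus sign restored only, L <= -14.5 | 95.1% | 12.6% | 0.1% |

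**Sensitivity at the margin.** With 126 per arm (140 x 0.9): (a) 5.1%, (c) 100%, (d) 99.9%, (e) 94.9%. With Wald at 128: (a) 4.9%, (c) 100%, (d) 99.9%, (e) 95.1%. The pattern does not depend on the method or on these sample sizes.

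**Two worked outcomes.** The hybrid score uses each arm's 90% Wilson limits (l, u): L = d - sqrt((p1 - l1)² + (u2 - p2)²) and U = d + sqrt((u1 - p1)² + (p2 - l2)²), where d = p1 - p2. For the comparator, 81/128 = 0.6328, with Wilson limits 0.5607 and 0.6995.

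1. Angal 62/128 = 0.4844 (Wilson 0.4128, 0.5566), d = -0.1484. L = -0.1484 - sqrt(0.0716² + 0.0667²) = -0.246; U = -0.1484 + sqrt(0.0722² + 0.0721²) = -0.046. Both limits are below 14.5%, so the sentence is satisfied on either limit. L is below -0.145, so H0 is not rejected.
2. Angal 88/128 = 0.6875 (Wilson 0.6168, 0.7504), d = 0.0547. L = 0.0547 - sqrt(0.0707² + 0.0667²) = -0.0425; U = 0.0547 + sqrt(0.0629² + 0.0721²) = 0.1504. H0 is rejected, yet U exceeds 14.5%, so reading (d) denies non-inferiority.

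**The case against.** The strongest reply is that nobody would misapply the rule. The signed hypotheses are stated in the synopsis, Protocol 9.2 and SAP 3.9; the lower limit is named in Protocol 9.3, SAP 3.10 and SAP 4; the synopsis says that rejecting H0 gives the conclusion; and the sample-size program input in Protocol 9.2 pairs a lower limit with -0.145. The sentence also has one workable reading. If the difference is the comparator's advantage, as the worded hypotheses suggest, then an upper limit of 14.5% or lower is exactly right, as row (b) shows. On this view 14.5% is simply a margin written without its sign. Reading (d) is excluded by the sections that name the lower limit, reading (e) appears nowhere in the plan, and reading (c) would be noticed at once.

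Most of this stands. The intent is recoverable, and the large percentages must not be taken as the trial's expected type I error. Two points do not fall away. The plan defines no comparator-minus-Angal difference, and that reading needs the upper limit where three sections name the lower one. And combining the sentence with the parts of the plan that are defined gives reading (c), so the intended rule is reached only by overriding the sentence or by changing its scale. The one-sided Fisher test does not settle the matter either: in its standard form it tests a zero difference, not -14.5 points.

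**Conclusion.** The concern holds. The sole numeric criterion for the primary interval, present in both documents, contradicts H0 on the only signed scale the plan defines. At the margin the H0-matching rule succeeds 4.9% of the time, against 95.1% to 100% for the literal and sign-only readings on p1 - p2. These figures assume 128 per arm, a 63% comparator rate and the Newcombe hybrid score; Wald limits and 126 per arm give nearly the same values. Because the sentence governs the primary conclusion, it must be corrected before the primary analysis, even though the intended rule can be inferred.

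**What to change.** In Protocol 9.1.2 and SAP 4.1.2, replace the sentence with: *Non-inferiority is concluded if the lower limit of the two-sided CI for p(Angal) - p(ANTI-ANGIN) is greater than -14.5 percentage points.* Name one interval method in place of the citation. Use the same direction in SAP Figure 2 and mark -14.5 on it.

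In the same edit, put the margin into the worded hypotheses of Protocol 9.1.2, which omit it. Drop the one-sided Fisher test as the test of the non-inferiority null, or replace it with a margin-based test of H0: p1 - p2 <= -0.145.

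**Cost.** The correction is wording only. At the stated 90% level it needs no extra patients, and power at 65% v 63% is 87.4% with 128 per arm.

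A separate conflict decides the interval level. The synopsis plans for "A number of patients required at 80% power and 2.5% one-sided significance level", and Protocol 9.2 and 9.3 also use 0.025, while SAP 3.10 uses 0.05. One-sided 0.05 goes with the 90% interval and 0.025 with a 95% interval. If 0.025 is chosen, power at 65% v 63% is 79.2% with 128 per arm and 78.9% with 126 (hybrid score; Wald 78.8% and 78.3%). Reaching 80% would then take 131 (hybrid score) to 133 (Wald) evaluable per arm. That is 131/0.9 = 146 to 133/0.9 = 148 randomized per arm, against 140 planned; the alternative is to accept about 79%. That cost belongs to the choice of alpha, not to correcting this sentence.

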### 9.1.3 Analysis of the secondary efficacy endpoints

- The frequency of ≥50% total score reduction according to the TSS questionnaire completed by the Investigator as compared to the baseline in both Angal and ANTI-ANGIN® FORMULA groups at Visit 2 (Day 4).
- Total score reduction according to the TSS questionnaire, as well as a reduction in the symptoms (sore throat, difficulty in swallowing, salivation, erythema, and fever) after a 3-day therapy, at Visit 2 (Day 4), as compared to the baseline total score.
- A period of time required for disease symptoms relief, determined according to the patient's diary (subjective patient's evaluation), but no more than 5 days during the trial—for patients who have achieved the corresponding outcome.
- A proportion (%) of patients who fully recovered by Day 4 in Group A and by Day 5 in Group B (the outcome of a disease according to the objective evaluation by the Investigator, the total score according to the TSS questionnaire  $\leq 2$ ).
- A change in the sore throat intensity by 100 mm VAS (visual analogue scale filled in by the patient) at the beginning, after 3 days of therapy, and at the end of treatment in both groups.

The following statistical analysis methods are stipulated for the secondary efficacy endpoints:

• The frequency of ≥50% total score reduction by the TSS questionnaire completed by the Investigator relative to baseline in both Angal and ANTI-ANGIN® FORMULA arms at Visit 2 (Day 4)—the response frequencies will be compared in each time point using the Fisher's exact test.

- Total score reduction by the TSS questionnaire, as well as reduction in symptoms (sore throat, difficulty in swallowing, salivation, erythema and fever) after 3-day therapy, at Visit 2 (Day 4), relative to baseline total score—the between-arm comparison will be carried out using the Mann–Whitney test due to non-symmetrical nature of the scores distribution in the TSS scale.
- A period of time required for the symptoms resolution defined by the patient's diary (subjective patient's evaluation), but not more than 5 days within the trial (for patients who achieved the relevant outcome)—the between-arm comparison will be carried out using t-test or the Mann–Whitney test depending on the distribution character. The survival will not be evaluated due to low duration of the trial.
- The proportion (%) of patients who fully recovered on Day 4 in Group A and on Day 5 in Group B (disease outcome according to the objective evaluation by the Investigator, the total score by the TSS questionnaire  $\leq 2$ )—the between-arm comparison will be carried out using the Fisher's exact test.
- A change in the sore throat intensity by 100 mm VAS (visual analogue scale filled in by the patient) at the beginning, after 3 days of therapy, and at the end of treatment in both groups—the between-arm comparison will be carried out using the t-test.

A secondary endpoint analysis will be conducted both for the ITT (main analysis) and PP populations (additional analysis).

# 9.1.4 Safety parameters analysis

A descriptive part of the safety analysis will include an evaluation of incidences and two-sided CI 95% for the following parameters in every trial group:

- AEs: the incidence in total and for separate categories (according to MedDRA), for the trial and by groups;
- SAEs: the incidence in total and for separate categories (according to MedDRA), for the trial and by groups;
- Incidence of clinically significant changes of the physical examination results by visits and groups;
- Incidence of clinically significant changes of the laboratory results by visits and groups;
- Incidence of clinically significant changes of the vital signs (body temperature, BP, pulse rate, HR) by visits and groups;
- Incidence of clinically significant changes of the ECG parameters by visits and groups;
- Global tolerance evaluation during the trial by the Investigator and patient;

The Fisher's exact test will be used to compare incidences between the groups, and chi-square will be used to compare the global therapy tolerability by the Investigator and patient. The McNemar's test will be used to evaluate for the dynamic changes during the trial (before–after) for all the repeatedly evaluated incidences in every group.

In addition to the incidence, all the quantitative safety parameters will be presented in a table form (laboratory data, vital signs, ECG) by visits and groups. The difference will be evaluated using 2-way-ANOVA (group and visit numbers will serve as the relevant factors). The post-hoc criteria will be used in case of significant difference.

Safety analysis will be performed on the safety population.

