# 1 Introduction

This trial has been designed and conducted to evaluate the therapeutic efficacy and safety of the study drug Angal, lozenges [menthol], 1.0 mg + 5.0 mg (Sandoz d.d., Slovenia), comparing to ANTI-ANGIN® FORMULA, lozenges, 0.2 mg + 2.0 mg + 50 mg (OOO Valeant, Russia), in the treatment of patients with uncomplicated acute infectious and inflammatory diseases of the pharynx accompanied by a sore throat. The objective of this Phase III trial is to demonstrate the non-inferior therapeutic efficacy of the study drug as compared to the reference product.

This Statistical Analysis Plan was developed in accordance with the following documents:

- Guidelines for examination of medicinal products, Vol. 1. Federal State Budgetary Institution Scientific Center for Expert Evaluation of Medicinal Products under the Ministry of Health of the Russian Federation (eds. A.N. Mironov). Moscow: Grif and K, 2013.
- ICH harmonised tripartite guideline. Statistical principles for clinical trials (E9). Current Step 4 version dated 5 February 1998.
- GCP rules of the Eurasian Economic Union (a draft).

The objective of this Statistical Analysis Plan is more detailed, compared to Section 9 of the trial protocol, description of the main principles of the protocol-based statistical analysis, description of the primary and secondary endpoints analysis methods, as well as other data obtained during the trial.

This Plan stipulates for consistence of the scheduled and conducted statistical analysis to the trial protocol, including definition of the analysis data sets, transformations and calculations for the endpoints, observations quantity needed, etc. No changes in this Statistical Analysis Plan compared to the trial protocol are envisaged.

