# 4.1.1 Descriptive statistics

Descriptive statistics for the initial data (obtained during Visit 1) for all randomized patients will be presented for the following variables:

- Age (a number of complete years as at Visit 1 date based on the date of birth);
- Sex, race;
- Social habits;
- Vital signs: initial systolic blood pressure, diastolic blood pressure, breathing rate, body temperature;
- Physical examination (presence/absence of deviations from the reference for organs and organ systems);
- Hematology, biochemistry;
- Electrocardiogram: presence/absence of deviations;
- Throat pain intensity according to VAS;
- TSS evaluation;
- Symptoms duration (calculated as a number of days as at Visit 1 date based on the first signs occurrence date);

- Time since the diagnostics to the therapy initiation (calculated as a number of days as at Visit 1 date based on clinical diagnostics date);
- Concomitant diseases: rate for the main organs and systems (MedDRA terms);
- Concomitant therapy: rate for the main drug groups;

Descriptive statistics for the data obtained by Visits 2 and 3 will be presented for the following variables:

- Vital signs: systolic blood pressure, diastolic blood pressure, breathing rate, body temperature;
- Physical examination (presence/absence of deviations from the reference for organs and organ systems);
- Throat pain intensity according to VAS;
- TSS evaluation;
- Evaluation of therapy efficacy;
- Hematology, biochemistry;
- 12-lead ECG;
- Global evaluation of treatment tolerability;
- Compliance evaluation;

All the AEs and SAEs registered during the trial will be classified according to MedDRA terms. A percantage of patients with the registered AEs with relevant codes (according to MedDRA terms and term groups) will be presented for every trial arm. In addition, AEs will be classified for severity and relationship with the study drug/comparator drug.

Descriptive statistics will be presented for all parameters for each group separately.

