# Table 12.A number of patients with normal and abnormal hematology parameters (Visits 1, 2, 3)

Arm	Parameter	Hemoglobin	RBC	ESR	WBC
	Reference				
	Deviation				
	Reference				
	Deviation				

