# Table 14. A number of patient with normal and abnormal biochemistry parameters (Visits 1, 2, 3)

Arm	Parameter	Total protein	ALT	AST	Total bilirubin
	Reference				
	Deviation				
	Reference				
	Deviation				

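### The SAP never tabulates the incidence of clinically significant changes that Protocol 9.1.4 specifies for four safety domains, and its by-visit laboratory and ECG counts compare unlike parts of the two arms

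*Protocol*

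**What the plan says.** Protocol 9.1.4 lists four incidences of the same kind, each to be reported with a two-sided 95% CI. The laboratory one reads "Incidence of clinically significant changes of the laboratory results by visits and groups". The other three apply that definition to physical examination, vital signs and ECG.

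The same section assigns Fisher's exact test to between-group comparisons of incidences and McNemar's test to before-after changes within a group. Protocol 9.1 leaves the full analysis to the SAP.

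The SAP defines the categorical results differently. Section 4.1.1 gives the baseline ECG variable as "Electrocardiogram: presence/absence of deviations" and treats physical examination in the same way. Laboratory counts are in Tables 12 to 14, for example "A number of patient with normal and abnormal biochemistry parameters (Visits 1, 2, 3"), with rows Reference and Deviation. Table 8 uses the same two rows for ECG. Table 7 gives vital signs as means, medians and other continuous summaries.

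SAP Section 1 states: "No changes in this Statistical Analysis Plan compared to the trial protocol are envisaged".

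**The concern.** A deviation from reference and a clinically significant change are different events. The first requires neither clinical importance nor any change since Visit 1. If the shells are programmed as written, the report will contain counts under one definition while the protocol promised another, and nothing in the SAP tells the reader so.

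At stake is the protocol's own safety measure. Comparing safety between the arms is a secondary goal (Protocol 3.2), and the statistical objective in Protocol 9.2 names safety beside efficacy. If the rule for counting these events is settled only after an open-label trial has been read, it can be questioned. The by-visit layout adds a second difficulty, because the two arms do not contribute comparable patients to the laboratory and ECG data at Visits 2 and 3.

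**Working it through.** The plan states no figure on this point to reproduce, so the check compares the texts and then counts denominators.

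**Step 1. Domain by domain.**

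| Domain | Protocol 9.1.4 | SAP output |
|---|---|---|
| Physical examination | clinically significant changes | deviation present or absent (4.1.1); no shell in 5.1 |
| Laboratory | clinically significant changes | Reference / Deviation per visit, Tables 12–14 (4 + 8 + 4 = 16 columns) |
| Vital signs | clinically significant changes | continuous summaries (Table 7) and comparisons of changes (4.1.5); no count |
| ECG | clinically significant changes | Reference / Deviation per visit, Table 8 |

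Result: none of the four protocol incidences has a SAP output. Section 4.1.5 mentions the incidence of ECG changes but does not require clinical significance, and the only ECG shell behind it is Reference/Deviation.

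**Step 2. Do the two definitions count the same patients?** They need not.

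- Outside reference at Visit 1 and unchanged at Visit 2, judged unimportant: a Deviation at Visit 2, but not a protocol event.
- Newly outside reference, judged unimportant: a Deviation, but not a protocol event.
- A change the investigator judges important while the value stays inside reference: not a Deviation, but a protocol event.

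**Step 3. Where clinical significance survives.** SAP 3.6 has the investigator judge abnormal test results and register adverse events. Protocol 8.3.4 makes an abnormal result an adverse event if it causes clinical signs, is clinically significant or needs therapy, and requires clinically significant laboratory abnormalities at the last visit to be documented as adverse events. These cases reach SAP Tables 21 to 23, which are laid out by organ system or nosological group. They give no incidence per domain, no visit and no before-after comparison, and SAP 4.1.4 tests adverse events with Pearson's chi-squared.

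**Step 4. Who is in the laboratory and ECG counts.** Protocol Table 1 and SAP 3.8.2 schedule Visit 2 hematology, biochemistry and ECG for all Group A patients, but in Group B only for those with total TSS of 2 or less. Visit 3 is for unrecovered Group B only. Take 140 randomized per arm, ignore withdrawals, and let r be the share of Group B recovered at Visit 2.

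| Assessment | Group A | Group B |
|---|---|---|
| Visit 2 | 140 | 140 × r (recovered only) |
| Visit 3 | 0 | 140 × (1 − r) (unrecovered only) |
| End of treatment | 140 | 140 × r + 140 × (1 − r) = 140 |

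The documents give no value for r; the 63% in Protocol 9.2 is for absence of sore throat, not for total TSS of 2 or less. For any r below 1, a Visit 2 comparison sets a whole arm against a part selected on outcome, and at Visit 3 no between-arm comparison exists. Only the end-of-treatment row restores both arms.

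Physical examination at Visit 2 covers both groups. For vital signs the protocol is not consistent: Table 1 carries the restriction, while Section 4.2.4.2 lists them for everyone.

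**The case against.** The strongest reply is that little is lost. SAP 4.1.5 does analyse change: it compares vital-sign changes between groups, uses McNemar's test for repeated qualitative results and paired tests for quantitative ones, and adds ANOVA for group and time. A patient abnormal at both visits adds nothing to McNemar's discordant pairs, and the shells cover Visit 1 as well as later visits. Clinically significant results are captured as adverse events. The protocol calls these incidences descriptive, and SAP Section 4 rests the non-inferiority conclusion on the primary parameter alone.

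Most of this stands as a limit on how far the point goes. It does not close the gap: McNemar's test works within an arm and on crossing a reference limit, and neither it nor the adverse event tables gives the named incidence by domain and visit.

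A reader might also infer that routine out-of-range values will swamp the SAP counts. With 16 laboratory columns treated as independent, 1 − (1 − q)^16 gives 33% of patients with at least one flag at q = 2.5% and 56% at q = 5%. The documents do not support that as a magnitude:

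- The flag rates are assumed, and the columns are not independent (total neutrophils is listed beside its components).
- No SAP table reports whether a patient had any flag; each parameter is counted separately.
- Non-inclusion criteria 9 and 19 exclude leukocytosis, neutrocytosis, left shift, ESR above 30 mm/h and hemoglobin below 120 g/l, which removes much of the infection-related abnormality at baseline.

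Nor should one infer that vital signs are counted as out of range. Their incidence is simply absent.

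**Conclusion.** The point holds as a mismatch between the two documents. All four incidences of clinically significant change in Protocol 9.1.4 lack a SAP output, and the SAP declares no departure. For laboratory results, ECG and physical examination a different event is counted; for vital signs there is no count. In addition, the by-visit laboratory and ECG layout does not compare like with like. The protocol's own by-visit listing shares that weakness.

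The consequence is limited. Clinically significant results are not lost, since they remain adverse events, and the primary non-inferiority conclusion is unaffected. No effect on reported rates can be sized, because the documents give neither an out-of-range rate, nor a rate of clinically significant change, nor the share of Group B recovered on Day 4. The conclusion rests on reading the SAP shells as the complete list of planned tables. It is worth correcting because it restores a stated measure at small cost.

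**What to change.** In SAP 4.1.5 and the table shells:

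1. For physical examination, laboratory results, vital signs and ECG, add the per-arm incidence of investigator-judged clinically significant change from Visit 1, with 95% CI and Fisher's exact test.
2. Base the between-arm comparison on the end-of-treatment assessment: Visit 2, or Visit 3 for Group B patients not recovered at Visit 2.
3. Show the by-visit counts descriptively, as the protocol lists them, with the denominator in each cell.
4. Keep Reference/Deviation as a supportive shift table from Visit 1 to end of treatment.
5. Record any remaining departure, with its reason, as Protocol 9.6 requires, and amend the statement in SAP Section 1 if one remains.

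The cost is SAP wording, shells and more output. Cells will be sparse, so the tests will have little power and the intervals will carry most of the information. End of treatment falls a day later for unrecovered Group B patients, which should be footnoted. Before adopting item 1, confirm that the eCRF records a clinical-significance judgement for vital signs and physical examination, because SAP 3.6 covers only test results. Reconcile Protocol Table 1 with Section 4.2.4.2 on who has vital signs measured at Visit 2.
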